3.4 Blinding and Randomization

The treatment in this study will be blinded to the subjects, investigators, any individual conducting the study (e.g., nursing and pharmacy staff) and clinical study personnel. Participants will be assigned to treatment by a randomization schedule developed and maintained by an independent statistician.

Participants are randomized to active or control, following an equal allocation to treatment arms, stratified by COVID-19 disease severity (severe or critical as defined in [Section 4.4](#)).

Study drug and placebo will be provided as blinded investigational product (IP) with appropriate labeling to link to the randomization code. Where required, safety personnel and/or investigator may be unblinded to a particular subject's treatment assignment to meet reporting requirements to Regulators.

A data management plan and statistical analysis plan will be approved by the sponsor prior to unblinding study data.

3.5 Data Safety Monitoring Board

A Data Safety Monitoring Board (DSMB) will be established to review the safety of IV Ampion as the study progresses. The DSMB will be primarily responsible for reviewing any serious Adverse Event (SAE) and other clinically important safety findings (e.g., discontinuations due to AEs) that may occur during the study.

3.6 Stopping rules

The entire study may be stopped under defined circumstances as outlined in [Section 6](#).

4 SELECTION OF PARTICIPANTS

4.1 Number of Participants

The trial is designed to enroll up to approximately 200 patients across two treatment arms (active or control), with a 100 subjects per arm, randomized 1:1 using a random allocation sequence stratified by COVID-19 disease severity (severe or critical). An interim analysis of the data is planned after 30 subjects (n=15 subjects per arm) to evaluate the relative effect. At the interim analysis, the sample size may be re-estimated to determine the additional number of patients for adequate power up to the 200 subjects.

The number of participants is selected based on the effects observed for the primary endpoint. A study recently reported in Lancet Respiratory Medicine with 243 hospitalized patients receiving the placebo for COVID-19 found 22% did not achieve day 28 ventilation-free survival (Lancet Respir Med 2021; [https://doi.org/10.1016/S2213-2600\(21\)00494-X](https://doi.org/10.1016/S2213-2600(21)00494-X)). In the AP-014 study, a lower rate (8%) was observed for subjects receiving inhaled Ampion. Assuming the same proportions (8% for Ampion and 22% for control) by Day 28, with 100 subjects per group, a two-sided 5% significance level, and using a z-test with unpooled variances, then under binomial enumeration the power to detect this difference is about 81.3%.

4.2 Recruitment Methods

Subjects will be recruited from the population being seen by Investigators at the clinical sites participating in the study.

4.3 Participant Characteristics

The participant population are those infected with SARS-CoV-2 that have developed severe or critical symptoms consistent with COVID-19 and require supplemental oxygen to maintain blood oxygen saturation levels. Treatment of COVID-19 depends on the stage and severity of disease with a hyperinflammatory state observed in the moderate to severe stages that are thought to lead to clinical respiratory complications and critical COVID-19 (Gandhi 2020). Treatment with immunomodulators at this point in the disease may be more effective than anti-viral treatments.

The population of participants with COVID-19 who require supplemental oxygen were selected for this study to evaluate the efficacy of Ampion as an immunomodulatory therapy that may improve the clinical outcome of the disease and may reduce mortality.

4.4 Inclusion Criteria

Patients should fulfill all the following inclusion criteria:

1. Male or female, ≥ 18 years old.
2. Diagnosed with COVID-19, as evaluated by laboratory diagnostic test or diagnosis based on radiological clinical findings.
3. Baseline severity categorization of severe or critical COVID-19 infection per FDA Guidance for developing drugs and biological products for COVID-19 (February 2021):
 - a) Severe COVID-19:
 - Symptoms suggestive of severe systemic illness with COVID-19, which could include shortness of breath or respiratory distress
 - Clinical signs indicative of severe systemic illness with COVID-19, such as respiratory rate ≥ 30 per minute, heart rate ≥ 125 per minute, $\text{SpO}_2 \leq 93\%$ on room air at sea level ($\text{SpO}_2 \leq 90\%$ at altitude) or $\text{PaO}_2/\text{FiO}_2 \leq 300$
 - b) Critical COVID-19:
 - Oxygen delivered by high-flow nasal cannula (heated, humidified, oxygen delivered via reinforced cannula at flow rates > 20 L/min with fraction of oxygen ≥ 0.5) or
 - Non-invasive mechanical or endotracheal mechanical ventilation
4. Informed consent obtained from the patient or the patient's legal representative.

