1 PROTOCOL SUMMARY

1.1 Protocol Synopsis

Sponsor: Ampio Pharmaceuticals, Inc.	Investigational Product: Ampion™						
Title of Study: A Randomized, Double-Blinded, Placebo-Controlled Phase II Study to Evaluate the Safety and Efficacy of Intravenous Ampion in Adult COVID-19 Patients Requiring Oxygen Supplementation							
Rationale: The severe acute respiratory syndrome coronavirus 2 (SARS-CoV-2) has resulted in the pandemic spread of coronavirus disease 2019 (COVID-19), which has a high rate of infection, has a high rate of hospitalization, has overwhelmed healthcare systems, and can be fatal. Ampion is the low molecular weight filtrate of human serum albumin with the in vitro ability to modulate inflammatory cytokine levels. Ampion has the potential to improve clinical outcomes for COVID-19 patients by reducing inflammatory cytokines correlated with the disease. This study aims to evaluate Ampion and clinical outcomes in patients with COVID-19 who require supplemental oxygen. The data from this study will inform decisions for the Ampion clinical development.							
Lead Investigators: [name], PhD, USA							
Number of Sites: Approximately 10 sites							
Indication: Adult COVID-19 patients on supplemental oxygen							
Number of Participants: Sample size is approximately 200 patients, randomized 1:1 for Ampion or control. An interim analysis will be conducted at 30 participants, randomized 1:1 for Ampion or control to allow for sample size re-estimation as needed.							
Treatment Groups: There are two planned treatment arms:							

Treatment Arm	Investigational Treatment	

Active	IV Ampion for 5-days	

Control	IV Placebo for 5-days	

		Treatment Arm	Investigational Treatment	Active	IV Ampion for 5-days	Control	IV Placebo for 5-days
Treatment Arm	Investigational Treatment						
Active	IV Ampion for 5-days						
Control	IV Placebo for 5-days						

Sponsor: Ampio Pharmaceuticals, Inc.	Investigational Product: Ampion™
Objectives and Endpoints:	
Objective	Endpoint
Primary	
Assess the effect of Ampion compared to placebo on prevention of need for mechanical ventilation or death	
Occurrence of mechanical ventilation or death by Day 28.
Secondary	

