
Diagnosis and Main Criteria for Inclusion:
 
1. Male or female, ≥ 18 years old2. Diagnosed with COVID-19, as evaluated by laboratory diagnostic test or diagnosis based on radiological clinical findings.3. Baseline severity categorization of severe or critical COVID-19 infection per FDA Guidance for developing drugs and biological products for COVID-19 (February 2021):
a) Severe COVID-19:
• Symptoms suggestive of severe systemic illness with COVID-19, which could include shortness of breath or respiratory distress• Clinical signs indicative of severe systemic illness with COVID-19, such as respiratory rate ≥ 30 per minute, heart rate ≥ 125 per minute, SpO₂ $\leq 93\%$ on room air at sea level (SpO₂ $\leq 90\%$ at altitude) or PaO₂/FiO₂ ≤ 300b) Critical COVID-19:
• Oxygen delivered by high-flow nasal cannula (heated, humidified, oxygen delivered via reinforced cannula at flow rates > 20 L/min with fraction of oxygen ≥ 0.5) or• Non-invasive mechanical or endotracheal mechanical ventilation4. Informed consent obtained from the patient or the patient's legal representative.	

Main Criteria for Exclusion:
 
1. As a result of the medical review and screening investigation, the Principal Investigator considers the patient unfit for the study and/or progression to death is imminent and inevitable irrespective of the provision of treatments.2. Clinical diagnosis of respiratory failure (therapy not able to be administered in setting of resource limitation)3. Shock defined by systolic blood pressure <90 mm Hg, or diastolic blood pressure <60 mm Hg or requiring vasopressors. Vasopressor therapy is exclusionary if used to treat shock. Subjects receiving low dose vasopressors to maintain renal perfusion are eligible.4. Multi-organ dysfunction/failure5. Patient has severe chronic obstructive or restrictive pulmonary disease (COPD) (as defined by prior pulmonary function tests), chronic renal failure (only exclusionary if subject is currently on renal replacement therapy, i.e., subjects receiving peritoneal dialysis, hemodialysis, ultrafiltration are ineligible), or significant liver abnormality (e.g., cirrhosis, transplant, etc.).	

Sponsor: Ampio Pharmaceuticals, Inc.	Investigational Product: Ampion™

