3 STUDY DESIGN

3.1 Study Design Overview

This is a Phase II randomized, double-blinded, placebo-controlled study to evaluate the safety and efficacy of IV Ampion in participants with COVID-19 who require supplemental oxygen.

Interested COVID-19 patients will sign the appropriate informed consent document(s) prior to completion of any procedures. The investigator will review inclusion and exclusion criteria prior to any invasive procedures. If the patient is eligible after this review, the site will perform the necessary, if any, study procedures to confirm eligibility.

Participants will be randomized 1:1 to active or placebo using a random allocation sequence stratified by disease severity. The general sequence of events during the treatment and assessment period:

- Complete baseline procedures and sample collection.
- Participants are randomized to Ampion or placebo.
- Participants receive study intervention (active or placebo) through IV infusion for 5 days.
- Complete safety monitoring, study procedures, and sample collection through Day 60.

All subjects receiving test product will also receive the standard of care (SOC) for COVID-19, which includes:

- Oxygen administration to maintain oxygen saturation of 90% or greater.
- Nursing physical that may include review of neurological; pulmonary; cardiac; gastrointestinal; and urinary assessment at least daily during treatment.
- Vital monitoring (heart rate, blood pressure, temperature, respiratory rate, SpO₂) at least daily during treatment.
- Telemetry monitoring to evaluate heart rhythm and rate.
- Diet as tolerated to satisfy nutritional needs.
- Treatments for COVID-19 symptoms including antibiotics, cough suppressants/expectorants, anti-coagulants, fever reducers/pain killers, anti-nausea drugs, and/or bronchodilators.
- Treatments for COVID-19 as approved by the FDA including expanded access, emergency, or compassionate use (i.e., remdesivir, dexamethasone, convalescent plasma).
- Medications will be recorded as concomitant medication, tabulated, and compared among groups.

The clinical effects, safety, and tolerability of treatment will be evaluated from baseline through Day 60. Evaluations at screening and during the 5-day treatment occur in person. Evaluations after the 5-day treatment to the end of the study (days 7 to 60) will typically occur via telephone contact unless the patient is in an inpatient setting.

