3.2.2 Secondary Objectives

The secondary trial objectives evaluate the efficacy of IV Ampion versus control in improving the clinical course and outcomes of participants with COVID-19 who require supplemental oxygen.

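### The inclusion criteria do not carry over the supplemental-oxygen requirement in the title, indication and section 4.3: the severe category can be met on room air.

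*Protocol*

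**What the plan says.** The descriptive text is consistent about who the trial is for. The title refers to "Intravenous Ampion in Adult COVID-19 Patients Requiring Oxygen Supplementation". The synopsis gives "Indication: Adult COVID-19 patients on supplemental oxygen". Section 4.3 says participants "require supplemental oxygen to maintain blood oxygen saturation levels". The secondary objectives (3.2.2) speak of "improving the clinical course and outcomes of participants with COVID-19 who require supplemental oxygen". Sections 2.4 and 3.1 use the same population, as do SAP sections 2, 2.2 and 2.3. The primary objective (3.2.1) differs: it names respiratory distress and does not mention oxygen.

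The operative list in section 4.4, and its copy in the synopsis, has four items: adult age, a COVID-19 diagnosis, a baseline category of severe or critical, and consent.

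- Severe (3a) requires compatible symptoms and clinical signs. The signs are given as examples joined by an *or*: "such as respiratory rate ≥ 30 per minute, heart rate ≥ 125 per minute", a room-air saturation of 93% or below at sea level, or a PaO2/FiO2 ratio of 300 or below.
- Critical (3b) is the only item that mentions oxygen delivery. It begins "Oxygen delivered by high-flow nasal cannula" and goes on to non-invasive and endotracheal ventilation.

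Section 9.2.2 and SAP 5.1.2 analyse efficacy in all randomised patients.

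**The concern.** Eligibility criteria decide whom a trial is about, and here the checkable list is wider than the stated population. A site that follows section 4.4 exactly can randomise a patient who is not on oxygen without breaching any criterion. Monitoring (10.7.1) verifies adherence to the inclusion and exclusion criteria, so it would not flag that patient.

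Three things are at stake.

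- **Applicability.** The result might not describe the patients named in the title and indication.
- **Endpoints.** A hospitalised patient on room air starts at 3 on the ordinal scale rather than 4 or above, and has no baseline oxygen flow for the oxygen-use endpoint to improve.
- **Power, conditionally.** Section 2.2 links oxygen need to the more severe cases, so a lower event rate in room-air patients is plausible, though the documents give no figure.

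Randomisation and efficacy summaries use only the severe/critical split (3.4, 9.3.1.5). Room-air patients would be neither balanced between arms by design nor reported separately. Removing them later would mean excluding patients after randomisation.

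**Working it through.** **Step 1: can criterion 3a be met on room air?** Take a breathless patient with a heart rate of 125 or more and normal saturation without oxygen. The symptom limb is met, and the heart rate is one of the listed example signs. A second case is a patient measured at 91-93% on room air at sea level. That reading meets the listed saturation sign and already lies within the standard-of-care target in 3.1, "Oxygen administration to maintain oxygen saturation of 90% or greater". Neither route needs the patient to be on oxygen.

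**Step 2: does anything else remove them?** None of the eleven exclusions in section 4.5 concerns the absence of oxygen. The investigator may judge a patient unfit (exclusion 1), but that is discretionary. Section 4.3 describes participants and is not part of the list that must be fulfilled.

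**Step 3: reproduce the planned power.** Inputs from sections 4.1 and 9.1 and SAP 2.4: control 22%, Ampion 8%, n = 100 per arm, two-sided 5%, unpooled z-test, binomial enumeration. Reject when |p1 − p2| / √[p1(1 − p1)/n + p2(1 − p2)/n] ≥ 1.96, and sum the joint binomial probabilities over the rejection region. Result: 81.28%, matching the stated 81.3%.

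**Step 4: hypothetical sensitivity.** Two inputs are assumptions that appear nowhere in the documents: the room-air share f (10-30%) and the room-air control event rate r (4-10%). Patients on oxygen are given 22%, and the risk ratio is held at 8/22.

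- Control rate: pC = (1 − f) × 22% + f × r
- Ampion rate: pA = pC × 8/22

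For f = 20% and r = 5%: pC = 0.8 × 22% + 0.2 × 5% = 18.6%, and pA = 18.6% × 8/22 = 6.8%.

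| f | r | pC | pA | Power, n = 100 per arm |
|---|---|---|---|---|
| 10% | 4% | 20.2% | 7.3% | 77.3% |
| 10% | 5% | 20.3% | 7.4% | 77.5% |
| 10% | 10% | 20.8% | 7.6% | 78.7% |
| 20% | 4% | 18.4% | 6.7% | 72.8% |
| 20% | 5% | 18.6% | 6.8% | 73.3% |
| 20% | 10% | 19.6% | 7.1% | 75.8% |
| 30% | 4% | 16.6% | 6.0% | 67.8% |
| 30% | 5% | 16.9% | 6.1% | 68.7% |
| 30% | 10% | 18.4% | 6.7% | 72.8% |

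**Step 5: would the interim re-estimation compensate?** SAP 6.1 enlarges the trial only when the multiplier σ(1 − σ) / [σ*(1 − σ*)] exceeds 1, where σ is the average of the two arms' rates and σ* its planning value. The SAP does not state σ*. Taking it from the planning rates, σ* = (22% + 8%)/2 = 15%. In the f = 20%, r = 5% case, σ = (18.6% + 6.8%)/2 = 12.7%. The multiplier is 0.127 × 0.873 / (0.15 × 0.85) = 0.87. That is below 1, so the rule leaves the sample size as it is.

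**The case against.** The strongest reply is that the intent is plain. Section 4.3 sits within the chapter on selecting participants and says the oxygen-requiring population was chosen deliberately. The title, indication and design overview agree. Criterion 3a speaks of signs in the plural and as examples, so the view that one sign suffices is a reading rather than a stated rule. Randomisation is 1:1 within severity strata and analysis is by intention to treat, so a few room-air patients would not bias the comparison. The sensitivity also runs in one direction: 3b admits patients already on endotracheal ventilation, who could raise the observed rate. And SAP 6.1 lets the sponsor alter the sample size if the rate assumptions fail.

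Much of this stands. Internal validity is not threatened, and the intent is not in doubt. But intent in descriptive text does not gate enrolment, and whether one sign or several are needed, none has to involve oxygen. The interim safeguard is thin: it comes at 30 patients, and the multiplier rule does not respond to a lower event rate. Only the sponsor's general discretion is left.

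A reader might infer more than the documents support on three points:

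- **That the planning rates belong to a different population.** The 22% source is described only as hospitalised placebo patients and the 8% source only as recipients of inhaled Ampion. Neither has a stated oxygen status, so no mismatch can be shown.
- **That a patient at 92% would be left without oxygen.** The 90% target sets a floor; it does not say oxygen is withheld above it. A room-air reading is also a measurement condition and does not say the patient stays on room air.
- **That every objective names oxygen.** The primary objective does not, although section 2.4 ties its outcome to patients who need oxygen.

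**Conclusion.** The point holds as a gap between the stated population and the operative criteria. Section 4.4 and the synopsis do not turn the supplemental-oxygen requirement into a criterion, the severe category can be met on room air, and no exclusion removes such patients. The intent-to-treat population may therefore include patients outside the population named in the title, indication, 2.4, 3.1, 3.2.2 and 4.3. The passages must be reconciled.

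It would be tempting to conclude that the enrolled population is a different one. The documents do not support that: the criteria permit room-air enrolment, and nothing shows how often it would happen.

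The stated 81.3% power is correct for its inputs and is not disputed. The fall to about 77-79%, 73-76% or 68-73% at room-air shares of 10%, 20% or 30% depends wholly on the assumed shares, the assumed 4-10% control rate and a constant risk ratio. It shows only that a design planned at 81.3% has little margin. The firm consequence is to whom the result applies.

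**What to change.** Add to section 4.4 and the synopsis a separate criterion that the patient is receiving supplemental oxygen at randomisation. Criterion 3 should stay in force beside it, both as an eligibility gate and as the definition of the severe and critical strata. If 3a were kept only to assign the stratum, a patient on low-flow oxygen who met neither 3a nor 3b would be eligible but have no randomisation stratum.

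Sites can check the criterion from the oxygen mode and flow rate and the ordinal score already recorded at Day 0 (5.1.2), so no new procedure is needed. Section 5.1.2 lists randomisation ahead of these items, whereas 3.1 puts baseline procedures first. The amendment should say that oxygen status is confirmed before randomisation.

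If the sponsor does intend to enrol room-air patients, section 4.4 can stand. The title, indication, 2.4, 3.1, 3.2.2 and 4.3, with the matching SAP text, should then be changed to describe the wider population.

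The cost is a short protocol amendment. With the added criterion, some patients who now qualify would be screened out, which may slow recruitment slightly. The stated sample-size inputs do not change.

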4.5 Exclusion Criteria

Patients fulfilling one or more of the following criteria may not be enrolled in the study:

1. As a result of the medical review and screening investigation, the Principal Investigator considers the patient unfit for the study and/or progression to death is imminent and inevitable irrespective of the provision of treatments.
2. Clinical diagnosis of respiratory failure (therapy not able to be administered in setting of resource limitation).
3. Shock defined by systolic blood pressure <90 mm Hg, or diastolic blood pressure <60 mm Hg or requiring vasopressors. Vasopressor therapy is exclusionary if used to treat shock. Subjects receiving low dose vasopressors to maintain renal perfusion are eligible.
4. Multi-organ dysfunction/failure.
5. Patient has severe chronic obstructive or restrictive pulmonary disease (COPD) (as defined by prior pulmonary function tests), chronic renal failure (only exclusionary if subject is currently on renal replacement therapy, i.e., subjects receiving peritoneal dialysis, hemodialysis, ultrafiltration are ineligible), or significant liver abnormality (e.g., cirrhosis, transplant, etc.).
6. Patient has chronic conditions requiring chemotherapy or immunosuppressive medication (only exclusionary if subject is currently receiving a high dose or therapy for transplantation, e.g., subjects receiving low dose inhaled or oral steroids for asthma are eligible).

7. A history of allergic reactions to human albumin (reaction to non-human albumin such as egg albumin is not an exclusion criterion) or ingredients in 5% human albumin (N-acetyltryptophan, sodium caprylate).
8. Prolonged QT interval.
9. Patient has known pregnancy or is currently breastfeeding.
10. Patient planning to become pregnant, or father a child, during the treatment and follow-up period and/or is not willing to remain abstinent or use contraception.
11. Participation in another clinical trial (not including treatments for COVID-19 as approved by the FDA through expanded access, emergency, or compassionate use), or participation in a trial such that enrollment in this study would fall within the time frame of the half-life of the other investigational product(s).

4.6 Inclusion of Patients Incapable of Giving Informed Consent

Patients who are not sedated or otherwise cognitively impaired may be capable of giving informed consent. In the remaining cases, patients will be enrolled in the study via their legally authorized representative (LAR) by telephone or in person. Enrolled via LAR by telephone requires confirmation of enrollment by two clinicians (e.g., registered nurse or physician).

